# 7.3.2 VP-315 Dosing Strategy

## **7.3.2.1** Study Part 1

In Part 1 of the study, the starting total daily dose for the evaluation of VP-315 will be 2 mg for the first subject. Subjects will receive ascending once-daily doses (increasing in 1-mg increments for up to 3 days in a 7-day treatment week [≥4 days off between treatment weeks]) until the first lesion is necrosed or until the subject experiences a DLT, whichever occurs first (Figure 7-2). Subjects will be observed for DLTs throughout the treatment period during Part 1.

After receiving a dose, the subject will return to the clinic the following day for assessment by the investigator. If, in the opinion of the SRC (see Section 7.4), there has been no DLT and if the lesion is not necrotic, the dose will be escalated, and the same lesion will continue to be treated before any additional target BCC lesions may be treated.

When a target lesion is deemed necrotic in the opinion of the SRC, the subject will not receive any additional treatment for that lesion, and a safety assessment visit will be performed instead. If the subject has additional lesions and no DLT has occurred, treatment of the next lesion may begin on day 1 (D1) of the next week. A maximum of 2 target BCC lesions may be treated, and only 1 lesion may be treated at a time. Subjects will be treated for a maximum of 2 weeks and a maximum total daily dose of 8 mg.

The starting dose will be escalated between subject cohorts in 1-mg increments after the previous cohort has completed Week 1 dosing (the DLT observation period) (Table 7-1). Dose escalation in Part 1 will end when 2 subjects experience a DLT at the same nominal dose (indicating that the preliminary MTD has been exceeded, and the preliminary MTD is the dose immediately below where any DLT occurred) or until a maximum VP-315 total daily dose of 8 mg is reached in up to 6 subjects.

## 7.3.2.2 Study Part 2

Part 2 will be initiated upon completion of Part 1 to determine the optimal dosing regimen of VP-315. There were no DLTs observed in Part 1 of the study and the maximum dose of 8 mg was achieved. Therefore, the dose to be evaluated in Part 2 will be a total daily dose of 8 mg in the following 5 Cohorts:

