## 2. Objectives and Endpoints

The following objectives and endpoints will be considered.

Part 1	
Primary Objectives	Endpoints

 
To assess the safety, tolerability, and maximum tolerated dose (MTD) of ascending dose strengths of VP-315
 
	
 
Discontinuations due to adverse events (AEs); occurrence of dose-limiting toxicities (DLTs)
 
Cutaneous Reaction Assessment (CRA)
 

Exploratory Objectives 
 
To evaluate the objective antitumor efficacy of VP-315
 
	
 
Histological clearance of treated lesion(s) at excision
 
Clinical clearance of treated lesion(s) as determined by visual assessment (no tumor seen upon visible inspection) at excision
 
Estimate of remaining tumor volume (necrotic cells:tumor cells) at excision
 
Estimate of reduction in tumor volume (necrotic cells:tumor cells) at excision*
 
Abscopal effect as determined by
 

	
clinical and histological clearance of nontreated lesions at excision
 
 
• Physician Global Assessment (PGA)
 

Part 2 (Cohorts 1 and 2)	
Primary Objectives	Endpoints

 
• To determine the optimal regimen for dosing 8 mg of VP-315 based on safety and tolerability
 
	
 
• Treatment-related AEs; treatment-related serious adverse events (SAEs); discontinuations due to AEs; occurrence of TRAEs of special interest
 
• CRA
 

Secondary Objectives	Endpoints

 
• To evaluate the antitumor efficacy of VP- 315
 
	
 
• Clinical clearance of treated lesion at excision as determined by visual assessment (no residual tumor seen on visual inspection)
 
• Histological clearance of treated lesion(s) at excision
 
• Abscopal effect as determined by clinical and histological clearance of nontreated lesions at excision if nontreated lesions exist
 
• Estimate of remaining tumor volume (necrotic cells:tumor cells) at excision
 
• Estimate of reduction in tumor volume (necrotic cells:tumor cells) at excision*
 
• PGA
 

Exploratory Objectives	Endpoints

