#### 3.1. Part 1 (N = 10)

Subjects are to receive VP- 315 via once-daily dosing, with a starting total daily dose of 2 mg for the first cohort, escalating in 1 mg increments for subsequent cohorts after the current cohort has completed Week 1 dosing (the DLT observation period) and no DLT is observed. The planned dosing regimen is a split dose of VP-315 for all treatments. The  $\leq 500\mu\text{L}$  ( $\leq 8$  mg) dose is to be divided into 2 injections given at least 15 minutes and no more than 30 minutes apart, with 30% ( $\leq 150\mu\text{L}$ ) administered in the first injection and the remaining 70% ( $\leq 350\mu\text{L}$ ) with the second injection.

Subjects are to be treated until the lesion is necrosed or a DLT occurs, for a maximum of 2 weeks (W1D1, W1D2, W1D3 and W2D1, W2D2, W2D3 – up to 6 total doses increasing from the starting dose in 1 mg increments) and a maximum total daily dose of 8 mg. If the treated lesion necrosed and the subject has additional lesions, treatment of the next lesion may begin on D1 of the next week. A maximum of 2 TLs may be treated, and only 1 lesion may be treated at a time. DLT or visual confirmation of necrosis of all TLs will result in termination of VP-315 dosing.

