### **5.5. Definition of Baseline and Treatment Groups**

Baseline is defined as the most recent non-missing value obtained prior to first injection of study treatment. Summaries will be provided for the following groups, unless limited to a subset of these groups elsewhere in this SAP:

- Part 1
- Part 2
  - Cohort 1
  - Cohort 2
  - Cohort 4
  - Cohort 4 Expansion
  - Cohort 5
  - Cohort 5 Expansion
  - Overall (i.e., Part 2 Total, Displayed Total, or Expansion Total)

No other group or subgroup analyses will be performed.

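### SAP 5.5 pools Part 1 across 2 to 8 mg, so no planned table shows tolerability, or the number of subjects exposed, by dose; the MTD conclusion is not affected

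*SAP*

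**What the plan says.** The Part 1 primary objective in SAP Section 2 is "To assess the safety, tolerability, and maximum tolerated dose (MTD) of ascending dose strengths of VP-315". Its endpoints are discontinuations due to AEs, DLTs and the Cutaneous Reaction Assessment (CRA).

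Dose varies in two ways (SAP 3.1, N = 10). Between cohorts, subjects are treated "with a starting total daily dose of 2 mg for the first cohort, escalating in 1 mg increments for subsequent cohorts". Within a subject, there are "up to 6 total doses increasing from the starting dose in 1 mg increments", capped at 8 mg a day.

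SAP 5.5 lists the reporting groups. Part 1 is one group, and only Part 2 is divided by cohort. The list applies "unless limited to a subset of these groups elsewhere in this SAP", which permits narrowing but not a finer split. The section then closes the matter: "No other group or subgroup analyses will be performed".

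No later section brings dose back:
- AE and DLT tables are by system organ class and preferred term (SAP 9.1).
- Blood pressure is by timepoint, injection and visit (SAP 9.3).
- CRA is by visit and lesion (SAP 9.5).
- The exposure table summarises dose by visit, lesion and injection with descriptive statistics (SAP 7.6). It does not count subjects at each dose level.

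**The concern.** Dose strength is what Part 1 was set up to study, yet it appears in no Part 1 safety table. A pooled percentage over a four-fold dose range does not show whether events gather at the upper doses or are spread evenly. It also does not show how many subjects stand behind any statement about 8 mg. That matters because 8 mg is the target daily dose of every Part 2 cohort, and Protocol 2.3.2 bases that choice on Part 1. Under SAP 5.2, an analysis added after database lock must be labelled post hoc and exploratory. A by-dose safety table for a stated primary objective would then carry that label.

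**Working it through.** The plan gives no sample size calculation or power figure, so there is no figure to reproduce. Three checks apply.

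**1. How many dose levels are pooled.** Doses run from 2 to 8 mg in 1 mg steps: 8 − 2 + 1 = 7 levels, a ratio of 8/2 = 4, in 10 subjects.

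**2. Whether visit can stand in for dose.** By the SAP 3.1 rule, the dose on the k-th treatment day is min(8, start + k − 1) mg, for k = 1 to 6, if treatment is not stopped early:

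| Starting dose (mg) | W1D1 | W1D2 | W1D3 | W2D1 | W2D2 | W2D3 |
|---|---|---|---|---|---|---|
| 2 | 2 | 3 | 4 | 5 | 6 | 7 |
| 3 | 3 | 4 | 5 | 6 | 7 | 8 |
| 4 | 4 | 5 | 6 | 7 | 8 | 8 |
| 5 | 5 | 6 | 7 | 8 | 8 | 8 |

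A W1D1 row therefore mixes 2 mg with up to 5 mg or more, depending on which starting doses were used. The documents do not list these. The tables by visit (blood pressure, CRA, exposure) do not separate doses. A 2 mg starter ends at 7 mg and never receives 8 mg. Since the first cohort starts at 2 mg, not all 10 subjects can have been treated at 8 mg if the schedule was followed.

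**3. What the denominator does to the zero-DLT result.** For 0 events in n subjects, the exact 95% upper limit is 1 − 0.05^(1/n) one-sided and 1 − 0.025^(1/n) two-sided. The number treated at 8 mg is not given, so the smaller n are assumptions. Six is the ceiling in the protocol's rule for ending escalation, "until a maximum VP-315 total daily dose of 8 mg is reached in up to 6 subjects".

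| n | One-sided limit | Two-sided limit |
|---|---|---|
| 10 (pooled) | 25.9% | 30.8% |
| 6 | 39.3% | 45.9% |
| 3 | 63.2% | 70.8% |
| 2 | 77.6% | 84.2% |
| 1 | 95.0% | 97.5% |

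The observed DLT count is zero at every level whether pooled or split; only the precision changes. Discontinuations, Grade 2 or higher events, CRA and blood pressure events are not reported in the documents to be zero. For these, the distribution over doses is unknown as well.

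**The case against.** A reader might infer that the MTD objective itself cannot be answered. The documents do not support that. The rule is tied to dose: "Dose escalation in Part 1 will end when 2 subjects experience a DLT at the same nominal dose". Both documents record that no DLT occurred in Part 1 and that 8 mg was reached (Protocol 2.3.2, SAP 3.2). Zero DLTs overall is zero at each dose, so the rule was never triggered. In any case, escalation was decided during the study by the Safety Review Committee and its sub-committee (Protocol 7.4.1), not from end-of-study tables. This part of the objection stands in full.

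A reader might also see a conflict between protocol and SAP. There is none: Protocol 11.1 and 11.5.2 plan analysis by study part and leave further detail to the SAP. A dose split was allowed but never promised.

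Nor is the information lost. Dose with date and time of injection (SAP 7.6) and AEs with start date and DLT flag (SAP 9.1) are listed by subject, and for 10 subjects they can be matched. But the listed AE fields include no dose at onset, and the cohort field in the enrolment listing (SAP 7.1.1) names only Part 2 cohorts. Hand-matching is a poor substitute for a table on a primary objective.

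The strongest remaining point is against a naive by-dose table. Dose rises daily within a subject, so dose is confounded with treatment day and cumulative exposure. Protocol 2.3.1 reports that in an earlier LTX-315 study reactions lessened with further exposure. CRA is done before that day's injection (Protocol 8.4.6), so the same-day dose is not the one that produced the reaction. This does not remove the gap, but it means that the table needs an attribution rule and a caution.

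**Conclusion.** This is a reporting gap in an analysis choice. Up to seven dose levels in 10 subjects fall into one column, other groupings are ruled out, and tolerability by ascending dose cannot be read from any planned table. Neither can the number of subjects exposed at each dose. The MTD conclusion, that none was reached up to 8 mg, is untouched; what a pooled 0 of 10 overstates is the precision at the top dose. No remaining study decision hangs on the table, but the primary objective asks for it and the change is cheap, so it should be made.

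The dose paths assume that the SAP 3.1 schedule was followed without early stopping, and the numbers at 8 mg are assumed. The finding rests on the SAP text through Section 16; any table shells appended after it should be checked against Section 5.5.

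**What to change.** Keep the pooled Part 1 column. Amend SAP 5.5 to allow, for Part 1 only, a descriptive display by total daily dose (2, 3, …, 8 mg), as follows:

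- **Exposure:** the number of subjects treated at each level, used as the denominator.
- **Events:** treatment-emergent AEs, Grade 2 or higher events, DLTs, discontinuations due to AEs and blood pressure events. Attribute each to the most recent total daily dose received at or before onset. Keep the separate severity scale that SAP 9.1 uses for cutaneous injection site reactions.
- **CRA:** attributed to the last dose given to that lesion before the assessment.
- **AE listing:** add starting-dose cohort and dose at onset for Part 1.

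The rule should also say how to count an event on a treatment day when only the date is known, or when onset falls between the day's two injections.

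The cost is a few extra tables with sparse cells and overlapping denominators, since one subject contributes to several levels. A footnote should say that dose is confounded with treatment day and cumulative exposure. No inference is involved, so no multiplicity question arises. Made before database lock, the display avoids the post hoc label of SAP 5.2; made later, it should carry that label and is still worth giving.

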### **5.6. Handling Dropouts and Missing Data**

Unless described otherwise in other sections of this SAP, analyses will be carried out with the data available using no imputation for missing data.

### **5.7. Statistical Programming**

All analyses, tabulations, and validation programming will be performed using SAS version 9.4 or higher. Tables and listings will be presented in PDF format. SDTM datasets will be produced using Version 3.3 of the SDTM Implementation Guide. ADaM datasets will be produced using Version 1.1 of the ADaM Implementation Guide.

SDTM, ADaM, and tables will be validated by an independent programmer. The validation process will be used to confirm that statistically valid methods have been implemented and that all data manipulations and calculations are accurate. Checks will

be made to ensure accuracy, consistency with this SAP, consistency within tables, and consistency between tables and corresponding listings.

### **5.8. Coding Dictionaries**

Medical Dictionary for Regulatory Activities (MedDRA) version 24.1 will be used for coding adverse events and medical history excluding prior BCC treatment, procedures, and surgeries. World Health Organization (WHO) Drug Global B3 September 1, 2021 will be used for coding prior BCC medications and prior and concomitant medications. Dictionary up-versioning, if any, will be based on the most recently signed Data Management Plan (DMP).

### **5.9. Data Monitoring and Safety Review**

AEs, SAEs, DLTs, or TRAEs SI determined by the Investigator to be related to VP-315 administration should be reviewed by the SRC for each cohort initiated. The SRC should evaluate the adverse events for any safety implications of VP-315 and make recommendations regarding subsequent enrollment and dosing. Subjects experiencing a DLT or TRAE SI are to be discontinued from treatment per Section 10.2 of the protocol.

## **6. Analysis Populations**

**Enrolled Subjects:** Enrolled subjects are subjects who signed the informed consent form and were not screen failed. Enrolled subjects will serve as the population for certain analyses as described in this SAP.

**Safety (SAF) Population:** The Safety Population will include all subjects who received at least one injection of VP-315. The SAF Population will serve as the primary population for the analysis of safety-related data.

**Full Analysis (FA) Population:** The Full Analysis Population will include enrolled subjects who received one full dose (actual equals expected for at least one treated lesion) of VP-315 (for Part 1 and Part 2 Cohorts 4 and 5, a full dose consists of two injections) and have at least one non-missing post-baseline efficacy observation for histologic clearance of lesions at excision (see Section 8 of this SAP for details). The FA Population will serve as the primary population for the analysis of efficacy-related data.

**Per-protocol (PP) Population:** The Per-protocol Population will include FA subjects who have no major protocol deviations that may substantially affect the results of the efficacy analyses outlined in Section 8 of this SAP. The final determination on protocol violations, and thereby the composition of the PP, will be made before database lock.

The PP Population will be used as the secondary population for the efficacy analyses outlined in Section 8 of this SAP.

A non-exhaustive list of potential major protocol deviations is provided below:

- Investigational Product Deviations
  - Subject received wrong treatment
  - Deviation in IP storage
  - Error in IP dosing
- Enrollment Deviations
  - Subject is enrolled prior to determining whether eligible for study
  - Ineligible subject is enrolled
  - Enrollment occurs outside protocol window
- Study Data and/or Forms Deviations
  - Forms or data not sent from clinical site to coordinating center
  - Missing data and/or form
  - Missing images and/or operative reports
- Subject Deviations
  - Subject administration of a prohibited medication
  - Subject compliance with protocol
  - Subject met withdrawal criteria but was not withdrawn
- Visit/Procedure Schedule Deviations
  - Visit/Procedure not completed
  - Visit/Procedure not completed in window

**Pharmacokinetic (PK) Population:** The Pharmacokinetic Population will include SAF subjects who have at least one non-missing quantifiable observation (i.e., numeric) for LTX-315 (i.e., VP-315) concentration. Blood samples for PK assessments will only be collected for a subset of subjects in Part 2 Expansion Cohorts 4 and 5. The PK Population will be used for PK analyses.

Non-missing observations outside the limits of quantitation for LTX-315 concentration will be handled as follows:

- Observations < lower limit of quantitation (LLQ) will be assessed at  $0.5 \times LLQ$
- Observations > upper limit of quantitation (ULQ) will be assessed at ULQ

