- Part 1 (N= 2 to 8): VP- 315 once-daily dosing; starting total daily dose of 2 mg for the first subject. Ascending once-daily 1-mg dosing increments (e.g., 2 mg on Day 1, 3 mg on Day 2). Subjects may be treated for a maximum of 2 weeks and a maximum total daily dose of 8 mg in Part 1. The starting dose will be escalated between subject cohorts in 1-mg increments after the previous cohort has completed Week 1 dosing (the DLT observation period) (Figure 7-1 and Figure 7-2).
- Part 2 (N= Approximately 66 to 72): VP-315 once-daily dosing; will be a total daily dose of 8 mg in up to 5 cohorts (i.e. there were no DLTs that occurred during Part 1 and the maximum dose of 8 mg was achieved).
  - Cohort 1 (N=3-6): VP-315 once-daily dosing of 8 mg with a loading dose of half the target dose of 8 mg (i.e. 4 mg) only on W1D1; all remaining doses will be the full target dose without a loading dose. Subjects will be treated until the lesion is necrosed, for a maximum of 2 weeks (W1D1, W1D2, W1D3 and W2D1, W2D2, W2D3 up to 6 total doses).

Cohort 2 (N=3-6): VP-315 once-daily dosing of 8 mg on all treatment days (i.e., NO LOADING dose on W1D1) for up to 3 consecutive daily doses/week until the lesion is necrosed, for a maximum of 2 weeks (W1D1, W1D2, W1D3 and W2D1, W2D2, W2D3 – up to 6 total doses).

The study design and dosing strategy listed below for Cohorts 3, 4 and 5 are recommendations from the Safety Review Committee following an adhoc safety review meeting held on June 13-14, 2023 to discuss subjects reports of pain and burning at the injection site that were not observed in Part 1 of the study:

- Recommendation: Remove/skip Cohort 3 in Part 2 of the protocol and advance from Cohort 2 to Cohorts 4 and 5. Revert to Part 1 dosing strategy of a 30/70 split dose for all treatments with the injections 19dministered 15-minutes apart.
  - Cohort 3 (N=0)This cohort has been removed at the recommendation of the SRC. : This cohort has been removed upon the completion of Cohort 2.

For Part 2 (Cohorts 4 and 5) the highest total daily dose of VP-315 (8.0 mg) will be divided into a split dose; the first dose is not to exceed 2.4 mg (30% of 8-mg dose), and the remaining dose will not exceed 5.6 mg (70% of 8-mg dose) and administered 15 minutes apart (not to exceed 30 minutes).

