For Part 1 of this study, the highest proposed total daily dose of VP-315(8.0 mg), is broken into two administrations at least 15 minutes apart (not to exceed 30 minutes), with the first dose not to exceed 2.4 mg (30% of 8-mg dose), and the remaining dose will not exceed 5.6 mg (70% of 8-mg dose); both doses are well below the historical 8 mg maximum tolerated dose (MTD). Therefore, the maximum dose of VP-315 in the proposed study (8.0 mg) and maximum concentration (16.0 mg/mL) should be well within the safety limits established in the previous Phase 1 monotherapy study.

For Part 2 (Cohorts 4 and 5) the highest total daily dose of VP-315 (8.0 mg) will be divided into a split dose; the first dose is not to exceed 2.4 mg (30% of 8-mg dose), and the remaining dose will not exceed 5.6 mg (70% of 8-mg dose) and administered 15 minutes apart (not to exceed 30 minutes). This dosing strategy was selected as a recommendation from the Safety Review Committee following an adhoc safety review meeting held on June 13-14, 2023 to discuss subjects reports of pain and burning at the injection site that were not observed in Part 1 of the study:

• Remove/skip Cohort 3 in Part 2 of the protocol and advance from Cohort 2 to Cohorts 4 and 5. Revert to Part 1 dosing strategy of a 30/70 split dose with the injections adminstered 15-minutes apart.

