#### 11.3 Analysis Populations

The following populations will be used for the VP-315 study:

- The Safety Population will include all subjects who take at least 1 dose of VP-315. Safety analyses will be conducted using the Safety Population.
- Full Analysis Set (FAS): this set is a subset of all enrolled subjects, excluding subjects who do not receive at least 1 full dose of VP-315 and those with no assessment of histologic clearance. The FAS will serve as the primary population for the analysis of efficacy-related data.
- Per-protocol Analysis Set (PPS): this set is a subset of the FAS, excluding subjects with important protocol deviations that may substantially affect the results of the primary efficacy analyses. The final determination on protocol violations, and thereby the composition of the PPS, will be made before clinical database lock. The PPS may be used for supportive analyses.
- PK Analysis Set: this set consists of subjects in the Safety Population with at least 1 plasma sample with quantifiable concentration of VP-315.

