
 
• To assess the immune response to VP-315 treatment in a subset of subjects by assessing the immune repertoire in blood and in tissue
 
	
 
• Multiplex immunohistochemical staining for T-cell subsets and immune activation markers in tumor tissue samples
 
• Analysis of T-cell clonality in blood and tumor tissue samples
 

 
• To assess subject satisfaction with the treatment
 
	
 
• SCAR-Q, FACE-Q
 

Part 2 (Cohorts 4 and 5)	
Primary Objectives	Endpoints

 
• To gain additional information on the
 
	
 
• Treatment-related AEs; treatment-
 

Verrica Pharmaceuticals Inc.  
Protocol: VP-315-201

Statistical Analysis Plan  
6-Sep-2024

safety, tolerability, and dosing regimen of VP-315 to support a pivotal study protocol design	related serious adverse events (SAEs); discontinuations due to AEs; occurrence of TRAEs of special interest 
 
● CRA
 

Secondary Objectives	Endpoints

 
● To confirm the antitumor efficacy of VP-315 using the optimal dosing regimen determined in Part 2
 
	
 
● Clinical clearance of treated lesion at excision as determined by visual assessment (no residual tumor seen on visual inspection)
 
● Histological clearance of treated lesion(s) at excision
 
● Abscopal effect as determined by clinical and histological clearance of nontreated lesions at excision if nontreated lesions exist
 
● Estimate of remaining tumor volume (necrotic cells:tumor cells) at excision
 
● Estimate of reduction in tumor volume (necrotic cells:tumor cells) at excision*
 
● PGA
 

 
● To characterize the pharmacokinetics (PK) of an 8 mg dose of VP-315 administered with the optimal dosing regimen determined in Part 2.
 
	
 
● Plasma VP-315 concentrations
 

Exploratory Objectives	Endpoints

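### The PK Population is defined by a quantifiable result and not by dose received, so the 8 mg summaries can include a 2.4 mg exposure and leave out a fully dosed subject with no measurable drug

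*SAP*

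**What the plan says.** The secondary PK objective for Part 2, Cohorts 4 and 5, is stated as "To characterize the pharmacokinetics (PK) of an 8 mg dose of VP-315" (SAP section 2). For the daily dose in these cohorts, the protocol synopsis says "the first dose is not to exceed 2.4 mg (30% of 8-mg dose), and the remaining dose will not exceed 5.6 mg".

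The population for the PK analyses is set in SAP section 6: "The Pharmacokinetic Population will include SAF subjects who have at least one non-missing quantifiable observation (i.e., numeric) for LTX-315". The Safety Population on which it is built asks for very little: "The Safety Population will include all subjects who received at least one injection of VP-315". Protocol 11.3 agrees: "this set consists of subjects in the Safety Population with at least 1 plasma sample with quantifiable concentration of VP-315". In the same SAP section the Full Analysis Population does carry a dose condition, and the SAP notes that "for Part 1 and Part 2 Cohorts 4 and 5, a full dose consists of two injections".

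SAP section 6 also sets values below the lower limit of quantitation (LLQ) to half that limit, with no exception for the pre-dose sample. At the top it says "Observations > upper limit of quantitation (ULQ) will be assessed at ULQ". Neither limit is given. SAP section 12 summarises concentrations by timepoint and PK parameters in the PK Population, by expansion cohort and combined. The parameters come from an external vendor under a separate specification.

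**The concern.** Membership depends on the outcome being measured and ignores the exposure that the objective names. That works in two ways.

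First, one injection plus one quantifiable sample is enough. The protocol's text on managing treatment-related events (7.3.2.2) foresees dosing that stops after the first injection. For such a subject the first injection is also the last, so the post-last-injection samples follow 2.4 mg but are tabulated with those that follow 8 mg.

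Second, a fully dosed subject with no quantifiable sample is removed because of the result. That is the lowest exposure possible, and it is informative for a drug injected locally. The concentration listing uses the same population, so the result is missing there too.

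At stake is the description of systemic exposure in at most 20 subjects (protocol 8.4.8), in a study meant to inform a pivotal design.

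**Working it through.** **Inputs.** Daily dose 8 mg in 500 µL, split 150 µL and 350 µL (protocol 4.1); concentration 16 mg/mL (protocol 2.3.1); PK subset of up to 20 (protocol 8.4.8). Ten per expansion cohort is an assumption (an even split). The numbers of partly dosed and all-BLQ subjects are unknown, so one of each is used as an illustration.

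**The plan's own figure.** 0.30 × 8 mg = 2.4 mg, and 0.150 mL × 16 mg/mL = 2.4 mg. The remainder is 0.350 mL × 16 mg/mL = 5.6 mg. The split reproduces exactly.

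**Which samples are affected.** SAP section 12 lists 11 timepoints. Three come before the second injection (pre-dose, and 2 and 5 minutes after the first injection) and are valid for a subject stopped midway. The other eight (seven from 2 to 120 minutes after the last injection, and 24 hours) are not 8 mg samples for that subject.

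**Partly dosed subjects included.** Assume exposure proportional to dose, with k of n subjects at 30% of the full-dose exposure.
- Arithmetic mean ratio = (n − k + 0.3k)/n. For 1 of 20: 19.3/20 = 0.965 (−3.5%). For 1 of 10: 9.3/10 = 0.930 (−7.0%).
- Geometric mean ratio = 0.3^(k/n). For 1 of 20: 0.942 (−5.8%). For 1 of 10: 0.887 (−11.3%).
- Geometric CV: one such subject adds (ln 0.3)²/n to the log-scale variance. With an assumed true CV of 50%, the log variance is ln 1.25 = 0.223. For n = 20 it becomes 0.223 + 0.072 = 0.296, a CV of about 59%. For n = 10 it becomes 0.223 + 0.145 = 0.368, about 67%.

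**All-BLQ subjects removed.** If their true values are near zero, the reported arithmetic mean is too high by the factor n/(n − k). For 1 of 20: 20/19 = 1.053 (up to +5.3%). For 1 of 10: 10/9 = 1.111 (up to +11.1%).

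**Limit-of-quantitation rules.** A true-zero pre-dose value is raised by exactly 0.5 × LLQ. A post-dose BLQ value lies between 0 and LLQ, so the substitution is off by at most 0.5 × LLQ, in either direction. Capping at ULQ can only lower a peak, but by how much depends on unstated quantities. For a lognormal Cmax with an assumed geometric CV of 50%, the arithmetic mean falls by 23% if ULQ equals the median, 3% at twice the median and 0.5% at three times.

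**The case against.** Five points can be made for the plan.

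- *The scenario is narrow.* Sampling is tied to the first day of the full target dose, and the second injection may go ahead if a reaction during the first resolves within an hour. No partly dosed PK subject is shown to exist. This limits how often the problem can arise. But the tie to the full target dose fixes the sampling day; it does not exclude someone whose dosing stops on that day.
- *The information is reported elsewhere.* SAP 7.6 summarises actual dose per injection and lists whether the full dose was received. SAP 7.1.1 reports reasons for exclusion from the PK Population. Both cases are therefore traceable, but the PK summaries stay as they are.
- *The Full Analysis rule is a poor model.* It needs a full dose in at least one treated lesion, not on W1D1. That is correct, so the remedy should not simply borrow it.
- *Half-LLQ is a recognised convention.* SAP section 12 asks for geometric statistics at every timepoint, pre-dose included, and zeros would make these uncomputable. This stands, and a pre-dose rule has to deal with it.
- *Cmax and AUC follow a vendor specification that is not in the documents.* This also stands. A reader might infer that half-LLQ at 24 hours inflates AUC several-fold. Take a peak of 20 × LLQ two minutes after the last injection, a 60-minute half-life and the linear trapezoid. Carrying 0.5 × LLQ to 24 hours then gives 3.83 times the AUC to 120 minutes. Setting the 24-hour value to zero still gives 3.58, so most of that excess is interpolation across the 22-hour gap. Peak, half-life and LLQ are all assumed, and nothing shows that the vendor uses the substituted value.

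**Conclusion.** The population definition is a real weakness in both documents. It lets a 2.4 mg exposure into summaries meant to describe 8 mg, and it removes a fully dosed subject on the strength of the result. For the SAP's own concentration summaries this holds whatever the vendor does.

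The size is modest per subject: −5.8% or −11.3% on the geometric mean for one partly dosed subject among 20 or 10, and up to +5.3% on the arithmetic mean for one all-BLQ subject dropped from 20. The first pair rests on dose-proportional exposure, the last on true values near zero, and all on counts that nobody can know from the documents. The two effects pull in opposite directions, so no net bias can be claimed.

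A reader might go further and infer that the limit-of-quantitation rules distort both ends of the curve. The documents do not support that. Only the pre-dose shift of half the LLQ is certain. Nothing shows that any sample exceeds the ULQ or would go without re-assay, and the route from these rules to Cmax and AUC is unseen.

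**What to change.** In SAP section 6, define the PK Population as Safety Population subjects in the PK subset with at least one post-dose concentration result, quantifiable or BLQ. In SAP section 12:

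- Limit the 8 mg summaries of post-last-injection concentrations and PK parameters to subjects who received both W1D1 injections in full, using the Received Full Dose field already collected (SAP 7.6).
- Keep partly dosed subjects' pre-dose and post-first-injection samples where the first injection was given in full. List their later samples with the dose received.
- Show the number of BLQ and above-ULQ results at each timepoint.
- Report pre-dose BLQ as BLQ: zero for arithmetic statistics, geometric statistics not calculated.
- Flag Cmax and AUC as lower bounds for any subject with a value capped at ULQ.

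Ask that the vendor specification not carry 0.5 × LLQ into AUC after the last quantifiable sample. Record the departure from protocol 11.3 in SAP section 14.

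The cost is SAP wording and matching vendor instructions, with no new samples. The downside is that the 8 mg summary may lose a subject or two.
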